7.5 ASSESSMENT OF BIOLOGICAL MARKER

In this study, fecal calprotectin, eosinophil cationic protein (ECP) and eosinophil protein X (EPX) will be analyzed for all patients included in the study (with or without MC). For patients with confirmed diagnosis of MC these markers will be assessed at diagnosis and every 3 months up to month 24 (prospective component). The fecal samples will be analyzed by a Central Laboratory (Dept. de Farmacologia FMUP) using Quantum Blue. Report with the results will be provided to Investigators by mail.

7.5.1 Assessment of fecal calprotectin levels

The collected stools sample will be sent immediately to the laboratory at room temperature for extraction. Stools can be stored up to 6 days at room temperature. After 6 days, stools must be extracted. One gram of stool is enough for calprotectin detection.

Stools will be weighted and extracted with extraction buffer delivered with commercial kit.

After extraction and before storage, samples will be centrifuged (5min at 3000xg). Once centrifuged, supernatant must be transferred into a fresh tube. Undiluted extracts can be stored at -20°C for at least 4 months. Extracts must be diluted prior to analysis.

Calprotectin from diluted samples will be determined with an ELISA assay. Calprotectin wells are coated with monoclonal antibodies against calprotectin. Calprotectin present in patient samples binds to calprotectin antibody in the coating. After washing the unbound components, an anti-human calprotectin enzyme-labeled (calprotectin conjugate) is added to give a complex conjugate calprotectin antibody. After incubation, unbound conjugate is washed and removed, and the complex is incubated with a developing solution. Stops solution ends reaction and fluorescence in the wells is read. A standard curve allows the determination of calprotectin concentration in the sample.

7.5.2 Assessment of fecal EPC and EPX levels

Stools samples will be collected and immediately frozen at -20°C or stored in a refrigerator for a maximum of 12h before freezing. Later, feces samples will be thawed overnight in the refrigerator. Approximately 0.1–1 g of feces will be weighted and diluted five times by adding 4 volumes (vol/wt) of an extraction buffer. The mixture will be homogenized until a homogenous solution is obtained.

An aliquot of 0.5 ml of the homogenate will be diluted 20 times in extraction buffer. After incubation at 6°C for 30 min and mixing, the homogenate will be centrifuged at 2000xg for 30 min at 5°C. The supernatant without particles will be thereafter transferred to fresh tubes and frozen at -20°C for later analysis.

Eosinophil cationic protein (ECP) from fecal samples will be determined with a fluoroenzymeimmunoassay. Anti-ECP, covalently coupled to ImmunoCAP, reacts with the ECP in the patient sample. After washing, enzyme labelled antibodies against ECP are added to form a complex. After incubation, unbound enzyme-anti-ECP will be washed away and the bound complex will then be incubated with a developing agent. After stopping the reaction, the fluorescence of the eluate will be measured. To evaluate the test results, the response for the patient samples are transformed to concentrations with the use of a calibration curve.

Eosinophil protein X (EPX) will be determined as described for Eosinophil cationic protein (ECP).

8 ENDPOINTS

8.1 PRIMARY ENDPOINT

Number of patients with confirmed diagnosis of MC (any subtype) over the total number of colonoscopies performed in all patients included in the study.

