2 INTRODUCTION

2.1 MICROSCOPIC COLITIS

Microscopic colitis (MC) is a chronic inflammatory bowel disease, characterized by watery, non-bloody diarrhea with macroscopically normal colonic mucosa and typical microscopic features. Other clinical findings of MC may include nocturnal diarrhea, faecal incontinence, abdominal pain and mild weight loss.^{1,2}

No unifying mechanism has been identified as being responsible for the pathophysiological abnormalities found in MC and the disease is likely to have multifactorial causes.³ Several risk factors such as cigarette smoking, especially among young patients,⁴ have been shown to be associated with the increased incidence of the disease. Diversion of the fecal stream has sometimes resulted in histological improvements,⁵ suggesting that the disease is caused by an abnormal response to luminal antigens. A wide variety of drugs have been proposed as potential triggers or etiological factors for MC, but none has been conclusively implicated. These include the non-steroidal anti-inflammatory drugs (NSAIDs), proton pump inhibitors (PPIs), selective serotonin reuptake inhibitors (SSRIs) and statins. However, all these drugs are widely used, therefore, it is expected that patients with MC might frequently use them coincidentally. Some authors point out that drug-induced MC cases are more likely due to an idiosyncratic reaction.^{6,7}

The diagnosis of MC rests on characteristic pathological findings in biopsies from normal or oedematous colonic mucosa. Although the topographic distribution of MC remains controversial, rectal biopsies are not sufficient.^{6,8} Some studies demonstrate that biopsies from the right and transverse colon are necessary for the diagnosis of MC, while others demonstrate that biopsies from the descending and sigmoid colon suffice for diagnosing this disease.⁸⁻¹² However, colonoscopy should be preferred because it is essential to rule out malignant colonic disease. Diarrhea caused by other diseases should be excluded; these diseases include bile acid diarrhea, coeliac disease, and lactose malabsorption.¹³

Two distinct histological types of MC, lymphocytic colitis (LC) and collagenous colitis (CC), have been described, but overlapping features are often present; indeed, some authors think that LC and CC are two histological subtypes of the same disease.^{3,14}

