3 OBJECTIVES

3.1 PRIMARY OBJECTIVE

To determine the prevalence of microscopic colitis (MC) among patients who attend a specialist appointment with symptoms of chronic, watery diarrhea of unknown etiology for more than 4 weeks and undergo colonoscopy.

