4 STUDY DESIGN

This is a multicenter, cross-sectional, observational study aiming to determine the prevalence of MC among a consecutive sample of subjects who attend a specialist consultation with symptoms of chronic watery diarrhea. In addition, the study design contemplates a 24-month prospective component with repeated measures for all patients with confirmed diagnosis of MC.

There is no imposed experimental intervention or treatment in this study. All therapeutic decisions and management of subjects will be done according to routine clinical practice.

All subjects who meet eligibility criteria and give their written informed consent to participate will be consecutively enrolled and characterized regarding several socio-demographic and clinical characteristics of interest. All eligible subjects will undergo a colonoscopy according to the routine practice for this type of population (Figure 1). Colonic specimens from all segments will be collected for subjects with macroscopically normal colonoscopies as part of the differential diagnosis of MC. Subjects with abnormal findings in colonoscopy suggestive of disorders other than MC will not be included in the prospective component of the study. These patients will continue to be managed according to the center's routine procedures.

The subjects with confirmed diagnosis of MC (upon histology assessment) will be followed over a period of 24 months in this study in order to investigate the clinical and histological progression. The data collection time points over this period will reflect this routine schedule. According to previous epidemiological studies on MC, it is estimated that 10-15% of patients with chronic, watery diarrhea will have a confirmed diagnosis of MC.^{23,37}

Patients without confirmed histological diagnosis of MC will not be followed up during the prospective part of the study. These patients will continue to be managed according to the center's routine procedures.

Socio-demographic and clinical characteristics of patients without diagnosis of MC (either based on macroscopic or histological assessment) will be directly compared with MC patients.

Overall, 300 subjects will be included in this study. The recruitment period will last one year but may be extended if the target number of participants is not achieved within the defined timeframe.

A total of 10 centers in Portugal are expected to participate. Subject recruitment will be competitive across participating centers.

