 - number of stools per day (the mean number of stools and watery stools per day will be calculated by summing the number of stools [any type] and watery stool that occurred over the week before the time point of assessment divided by 7 days).
 - type of stool (1 to 7 - Bristol Stool Chart)
 - nightly diarrhea
 - urgency (0 = no urgency, 1 = need to defecate within 30 minutes, 2=immediate need to empty the bowel, 3 = fecal incontinence - have to go immediately to the toilette)

- difficulties staying continent with a respective bowel movement
- abdominal pain (0 = no pain, 1 = mild, 2 = moderate, 3 = severe pain)
- Laboratory parameters – hemoglobin, platelets, leukocytes, neutrophils, eosinophiles, basophiles, monocytes, lymphocytes, erythrocyte sedimentation rate (ESR), C-reactive protein (CRP), iron and transferrin.
- Concomitant medications
- Changes in concomitant illness (worsening of previous conditions, new condition)

At diagnosis of MC and every 3 months up to month 24:

- Fecal sample – for assessment of calprotectin, ECP and EPX levels.

In addition, at Month 24 only:

- Date of colonoscopy with sampling of colonic specimens
- Result of colonoscopy: normal/abnormal - describe
- Date and result of histological assessment :
 - Geboes Index (grade for each of the colon segments: rectum, sigmoid, descending, transverse and ascending) – see Section 7.4.2.
 - IEL in the surface epithelium (not observed, < 5 IEL/100 surface epithelial cells, > 5 and < 20 IEL/100 surface epithelial cells, ≥20 IEL/100);
 - Thickness of the subepithelial collagen layer (not observed, <5 µm; > 5 and < 10 µm; ≥ 10 µm).

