7.3 ENDOSCOPIC ASSESSMENT

All eligible patients will undergo a complete colonoscopy as part of the routine procedures for differential diagnosis. The findings of the colonoscopy will be collected into the eCRF.

During the complete colonoscopy biopsies will be taken from the colonic segments for histological examination – see section 7.4.

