9.2 SAMPLE SIZE

This study will include 300 patients with chronic diarrhea allowing the estimation of a prevalence of 10-15%^{23,37} with an error margin of less than 4.5% and with 95% confidence interval. Assuming the lowest rate of the prevalence interval (10%), approximately 30 patients with MC are expected to be followed in the prospective component study.

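### The primary prevalence divides patients by colonoscopies without limiting the count to the baseline examination, so as worded it would count the Month 24 repeats that only MC patients have

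*Protocol*

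**What the plan says.** Section 8.1 gives the primary endpoint as "Number of patients with confirmed diagnosis of MC (any subtype) over the total number of colonoscopies performed in all patients included in the study". The synopsis says the same. Neither restricts the count to the baseline or first colonoscopy.

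Section 7.1 lists, for Month 24, "Date of colonoscopy with sampling of colonic specimens". The appendix chart marks a colonoscopy at baseline for everyone and at Month 24 in the part reserved for MC patients. Under Section 4, patients without histologically confirmed MC are not followed, so they have no second scheduled colonoscopy.

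The primary objective (Section 3.1) is a prevalence among patients with chronic watery diarrhea "of unknown etiology for more than 4 weeks and undergo colonoscopy". The sample size section (9.2) also counts patients: "This study will include 300 patients with chronic diarrhea".

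On biopsies at baseline, Section 4 states: "Colonic specimens from all segments will be collected for subjects with macroscopically normal colonoscopies". Section 7.1 asks for sampling dates and histology under a heading for patients whose colonoscopy was macroscopically normal. Section 7.3 says "During the complete colonoscopy biopsies will be taken from the colonic segments for histological examination" and states no such limit. The appendix chart marks specimen collection and histology in the baseline column for all patients. Section 2.1 describes the diagnosis as resting on "biopsies from normal or oedematous colonic mucosa".

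**The concern.** A prevalence needs the same unit above and below the line. Here each non-case adds one procedure to the denominator, while each case adds one at baseline and a second if the Month 24 examination takes place. The ratio would therefore depend on how many cases are retained for 24 months, which has nothing to do with how common MC is at presentation.

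This is the only primary endpoint. Section 12.4 allows publication only once the study has ended and the analysis is complete, so the Month 24 colonoscopies will be in the database by then. One analyst could follow the wording and count them, another could follow the objective and leave them out. The two would report different primary results from the same data.

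**Working it through.** **Inputs**
- n = 300 patients; assumed prevalence p of 10% to 15%; margin below 4.5 points with a 95% confidence interval; about 30 MC patients at 10% (Section 9.2).
- One further colonoscopy per MC patient at Month 24 and none for the others (Sections 4 and 7.1, appendix).
- r, the share of MC patients who have the Month 24 colonoscopy. The protocol gives no figure, though Section 6.4 foresees early discontinuation. Values of 100%, 80% and 50% are assumptions.

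**Step 1: reproduce the stated precision.** Half-width = 1.96 × √(p(1 − p)/n).
- p = 10%: 1.96 × √(0.10 × 0.90/300) = 3.39 points.
- p = 15%: 1.96 × √(0.15 × 0.85/300) = 4.04 points.

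Both are below 4.5, and 10% of 300 is 30. The calculation in Section 9.2 holds, and it treats the denominator as 300 patients.

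**Step 2: apply the endpoint as worded.** With x = np cases, the patient-based prevalence is x/n. The literal ratio is x/(n + r·x) = p/(1 + r·p). The shortfall is r·p²/(1 + r·p).

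| Month 24 share r | p = 10% (x = 30) | Shortfall | p = 15% (x = 45) | Shortfall |
|---|---|---|---|---|
| 100% | 30/330 = 9.09% | 0.91 points | 45/345 = 13.04% | 1.96 points |
| 80% | 30/324 = 9.26% | 0.74 points | 45/336 = 13.39% | 1.61 points |
| 50% | 30/315 = 9.52% | 0.48 points | 45/322.5 = 13.95% | 1.05 points |

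**Step 3: compare with the random error.** At full attendance the shortfall is 0.91/3.39 = 27% of the half-width at 10%, and 1.96/4.04 = 49% at 15%. It is smaller than the planned margin, but it always acts in one direction and recruiting more patients would not reduce it.

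**Step 4: read the biopsy statements together.** Sections 4 and 7.1 tie sampling to a macroscopically normal colonoscopy. Section 7.3 and the appendix chart state no restriction. Section 7.1 codes the colonoscopy as normal or abnormal only, so it is unclear on which side the oedematous mucosa mentioned in Section 2.1 falls, and hence whether such a patient would be biopsied. No arithmetic is possible here: the documents give neither the share of abnormal colonoscopies nor the frequency of MC among them.

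**The case against.** The strongest defence is that the intention is clear. The prevalence part is described as cross-sectional, follow-up is an added component, and the objective and sample size are both per patient. A sensible analyst would take one diagnostic colonoscopy per patient. This largely stands: it makes the understatement conditional on a literal reading, and nothing in the protocol shows an actual plan to count Month 24 procedures. It does not rescue the wording. The protocol states the denominator explicitly, so this is not a detail left open for a later analysis plan.

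It is also fair that the 2.0-point figure needs both 15% prevalence and full Month 24 attendance. At 10%, the rate from which Section 9.2 derives its 30 patients, the gap is at most 0.9 points.

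On biopsies, it can be said that in Section 7.3 the reference to all eligible patients governs the colonoscopy, while the biopsy sentence stands apart and refers on to Section 7.4. That softens the conflict without removing it, since the appendix chart also shows no restriction.

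A reader might infer that unbiopsied patients are a second denominator error that lowers the prevalence. The documents do not support this. Section 3.1 defines the population as those who undergo colonoscopy, so patients with abnormal findings belong in the denominator. Section 4 expressly allows a patient to be classed as without MC on macroscopic grounds. Prevalence would be understated only if some of these patients had undetected MC. Section 2.1 characterises MC by normal-looking mucosa, and the abnormal findings listed in Section 7.1 are other causes of diarrhea. Oedematous mucosa leaves at most a borderline group of unknown size.

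**Conclusion.** The primary endpoint is worded wrongly and conflicts with Sections 3.1 and 9.2. Followed literally with n = 300, it understates prevalence by up to 0.9 points at 10% and up to 2.0 points at 15%, or by about 0.5 and 1.0 points if half of the MC patients have the Month 24 colonoscopy. These figures rest on the prevalence range in Section 9.2, one repeat colonoscopy per retained MC patient, and assumed attendance.

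Two further readings should be avoided. A reader might infer that the literal ratio falls as MC becomes more common. It does not: p/(1 + r·p) rises with p, and what grows with prevalence and retention is the shortfall. A reader might also add repeats after incomplete examinations to the count, but the protocol describes none.

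The differing biopsy statements are a separate, lesser inconsistency. They matter because they decide who can be found to have MC, but no size of bias can be given for them.

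**What to change.** In Section 8.1 and the synopsis, define the primary endpoint as the number of patients with MC confirmed at the baseline colonoscopy, divided by the number of included patients with a baseline colonoscopy. Count each patient once and state that Month 24 procedures are excluded. This changes one sentence in two places. It needs no extra data or procedures and leaves the sample size calculation as it is.

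Separately, reconcile Sections 2.1, 4, 7.1 and 7.3 and the appendix chart so that one statement says who is biopsied at baseline, and say how patients without biopsies are counted in the primary endpoint. Which statement to keep is for the sponsor. The cost depends on that choice: aligning the text with Section 4 is an edit only, whereas the unrestricted reading would mean 4 × 5 = 20 biopsies under Section 7.4.1 for each patient with an abnormal colonoscopy. Reporting how many patients had no baseline histology, and why, would let readers judge the remaining uncertainty.

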8.2 SECONDARY ENDPOINTS

- Proportion of patients with confirmed diagnosis of each subtype of MC (CC, LC and IC)
- Age, gender, BMI, smoking status, duration of symptoms, stool frequency and consistency (type), familial history of IBDs, comorbidities, previous pharmacological/ non-pharmacological therapies and laboratory parameters to be compared between MC patients and non-MC patients.
- Treatments (pharmacological/non-pharmacological) prescribed by specialist for patients with MC diagnosis
- Number of stools and type (Bristol stool form scale), urgency and abdominal pain over the last 7 days before each time point of assessment for patients with MC diagnosis.
- Proportion of MC patients with clinical remission at each data collection time point (month 3, 6, 9, 12, 15, 18, 21 and 24)
Clinical remission: mean of < 3 stools per day and mean of < 1 watery stool per day
- Proportion of MC patients with histological remission at month 24.
See section 8.3.2 for definition of histological remission
- Age, gender, BMI, smoking status, duration of symptoms, stool frequency and consistency, familial history of IBDs, age at diagnosis of MC, time to diagnosis of MC, comorbidities, pharmacological/non-pharmacological therapies, laboratory parameters and histological features, compared with clinical activity status (active/non active) described for patients with MC diagnosis.
- Age, gender, BMI, smoking status, duration of symptoms, stool frequency and consistency, familial history of IBDs, age at diagnosis of MC, time to diagnosis of MC, comorbidities, pharmacological/non-pharmacological therapies, laboratory parameters, compared with histological features, described for patients with MC diagnosis.
- Area under the ROC curve of fecal calprotectin, ECP and EPX levels with clinical activity at each data collection time points among MC patients.
- Area under the ROC curve of fecal calprotectin ECP and EPX levels with histological activity at each data collection time points among MC patients

For definition of clinical and histological activity see section 8.3.1 and 8.3.2.

8.3 DEFINITIONS OF INTEREST

8.3.1 Clinical outcomes (applicable to all MC subtypes – CC, LC and IC)

- **Clinical activity:** mean of ≥ 3 stools per day or mean of ≥ 1 watery stool per day.³⁸
- **Clinical remission:** mean of < 3 stools per day and mean of < 1 watery stool per day.³⁸

The mean number of stools and watery stools per day will be calculated by summing the number of stools (any type) and watery stool that occurred over the week before the time point of assessment divided by 7 days.³⁸

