7.2 SYMPTOMS ASSESSMENT

The symptoms will be assessed throughout 24 months (approximately every 3 months) for all patients with confirmed diagnosis of MC (any type). The symptoms include:

- Stool frequency (number of stools per day).
- Stool consistency (type of stool according to the Bristol Stool Chart – Figure 1)
- Nightly diarrhea
- Urgency (0 = no urgency, 1 = need to defecate within 30 minutes, 2 = immediate need to empty the bowel, 3 = fecal incontinence - have to go immediately to the toilette),
- Difficulties staying continent with a respective bowel movement (yes/no)
- Abdominal pain (0 = no pain, 1 = mild, 2 = moderate, 3 = severe pain)

The Bristol Stool Chart is used to monitor change in intestinal function and is widely used both in clinical practice and research. This scale classifies the form of human faeces into seven categories (figure 2).

[figure not shown]

Figure 2 – Bristol Stool Chart

During the first appointment of the study, the symptoms will be captured by the physician into the eCRF by interviewing all the eligible patients who will report to the previous 7 days. During the subsequent appointments the symptoms will **only** be recorded by the MC patients, using the patient diary. The patient diary should be completed on a daily basis for the period of 7 days before the next appointment to the specialist. The symptoms to be captured in the diary include the total number of stools and its type (according to Bristol Stool Chart) and therapies used (pharmacological/non-pharmacological) between appointments. The physician should clarify with the patient any inconsistency or missing information found in the patient diary.

The patient will be given at each appointment the necessary number of diaries to cover the period until the next scheduled appointment.

In case the patient forgets or loses the diary at one appointment, the investigator and the patient will have to estimate the number of stools and watery stools and this situation should be recorded in the eCRF (as estimated result) due to missing diary.

At each appointment, the investigator calculates the mean number of stools and of watery stools per day according to the formula:

The number of stools (any type) and watery stools in the week prior to the appointment will be divided by number of days with entries.

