The number of stools and the type will not be evaluable if less than 5 days of entries are found and there is no possibility to collect any further information regarding that week. The day corresponding to the preparation of endoscopy will not be used to assess these symptoms.

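### At follow-up, the mean stool count that decides clinical remission has two conflicting divisors (7 days, or days with entries), and the 7-day rule can move incomplete weeks near the threshold only towards remission

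*Protocol*

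**What the plan says.** Section 8.3.1 defines clinical remission as a "mean of < 3 stools per day and mean of < 1 watery stool per day"; reaching either limit is clinical activity. It obtains both means from the counts "that occurred over the week before the time point of assessment divided by 7 days". The follow-up part of section 7.1, which covers months 3 to 24, uses the same divisor: "watery stool that occurred over the week before the time point of assessment divided by 7 days".

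Section 7.2 gives the investigator a different formula for each appointment: "The number of stools (any type) and watery stools in the week prior to the appointment will be divided by number of days with entries". Three further rules in 7.2 bear on how many days there are:

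- Stool number and type "will not be evaluable if less than 5 days of entries are found" and nothing more can be learned about that week, so diaries with 5 or 6 entries are evaluable.
- "The day corresponding to the preparation of endoscopy will not be used to assess these symptoms".
- "The physician should clarify with the patient any inconsistency or missing information found in the patient diary". If the diary is forgotten or lost, an estimate is made with the patient and flagged in the eCRF.

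The baseline part of 7.1 also divides by 7, but those counts come from a physician interview about the previous 7 days, without a diary.

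**The concern.** Sections 7.1 (follow-up) and 8.3.1 on one side and 7.2 on the other govern the same visits and the same counts, and no section ranks them. The difference matters only when a week has fewer than 7 usable days, and 7.2 provides for such weeks. If 7 stays the divisor, a missing or excluded day adds nothing to the numerator but still counts in the denominator.

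The resulting label, active or in remission, is used in several secondary analyses (sections 8.2 and 9.1): the remission proportion at eight visits, the comparisons of patient characteristics by clinical activity, and the ROC analyses of calprotectin, ECP and EPX against clinical activity. Because 7.2 has the investigator calculate the mean, two sites could classify identical diaries differently and both be following the protocol.

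**Working it through.** **The plan's own figures.** The protocol calculates nothing that depends on the divisor. Its only calculated figures are in section 9.2, and they reproduce. The half-width 1.96 × √(p(1 − p)/300) is 3.39 points at p = 0.10 and 4.04 points at p = 0.15, both under the stated 4.5. The expected number of MC patients is 300 × 0.10 = 30.

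**Inputs.** S is the number of stools recorded in the week, W the number of watery stools, and d the number of usable days (5, 6 or 7 under section 7.2). The remission limits of 3 and 1 come from section 8.3.1.

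**The two rules.**

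- 8.3.1 and 7.1 (follow-up): remission if S/7 < 3 and W/7 < 1, that is S ≤ 20 and W ≤ 6.
- 7.2: remission if S/d < 3 and W/d < 1, that is S < 3d and W < d.

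**Where they disagree.** A week is in remission under the first rule and active under the second when S ≤ 20 and W ≤ 6 both hold and at least one of these bands is reached:

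| Usable days | Stools | Watery stools | Mean under /7 is lower by |
|---|---|---|---|
| 5 | 15–20 | 5–6 | 1 − 5/7 = 29% |
| 6 | 18–20 | 6 | 1 − 6/7 = 14% |
| 7 | none | none | 0% |

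Counts are whole numbers, so the highest recorded means that change class are 20/5 = 4.00 and 20/6 = 3.33 stools per day, and 6/5 = 1.20 and 6/6 = 1.00 watery stools per day.

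**Direction.** Going through every pair with S from 0 to 70 and W from 0 to S, 61 pairs disagree with 5 days, 33 with 6 and none with 7. All are remission under /7 and active under /d. This must be so: for the same counts, dividing by 7 can never give a larger mean than dividing by a smaller d.

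**Examples.**

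- 16 stools in 5 recorded days, none watery: 16/7 = 2.29 (remission); 16/5 = 3.20 (active).
- 6 watery stools in 5 recorded days, with few others: 6/7 = 0.86 (remission); 6/5 = 1.20 (active).

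**How much depends on closeness to the threshold.** The rates below are assumed, not taken from the protocol; counts are independent Poisson and the week has 5 entries. Both criteria are applied.

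| Assumed stools/day | Assumed watery/day | Chance of remission, /7 | Chance of remission, /5 |
|---|---|---|---|
| 2.5 | 1.0 | 0.76 | 0.40 |
| 3.5 | 1.2 | 0.54 | 0.14 |
| 5 | 3 | 0.007 | 0.001 |

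**Weight of one patient.** 1/30 = 3.3 percentage points of a visit's remission proportion.

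**The case against.** The best defence is that 7.2 is the working instruction. It alone is addressed to the person doing the calculation, and it stands beside the 5-day and preparation-day rules. The 7-day wording can then be read as describing a complete week, where the rules agree; 8.3.1 also speaks of stools that occurred, not stools that were recorded. This is a reasonable reading, but the protocol does not state it, and 8.3.1 is the endpoint definition.

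The second defence is repair. The physician clarifies gaps with the patient, and a missing diary is replaced by a flagged estimate. This will reduce the number of incomplete weeks. It cannot restore the preparation day, which 7.2 excludes outright.

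Stronger readings that a reader might infer, and that the documents do not support:

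- *Incomplete weeks are falsely scored as remission.* Only weeks in the bands above can change class, and only if the 7-day rule is applied. Calling the result false also assumes that unrecorded days resembled recorded ones.
- *Remission rates are inflated by a known amount.* The protocol gives neither the share of incomplete weeks nor the distribution of counts, so no study-level shift can be calculated.
- *The baseline divisor is part of the conflict.* The baseline interview covers 7 days without a diary, so dividing by 7 loses nothing.
- *The error is built in at month 24.* A colonoscopy is scheduled then, but the protocol does not fix whether the preparation day falls in the diary week. If it does, at most 6 days are usable.

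**Conclusion.** The contradiction is real and should be reconciled. Sections 7.1 (follow-up) and 8.3.1 fix one divisor and 7.2 fixes another, so the same evaluable week can receive two labels. A later analysis plan could choose between them, but the protocol does not leave the matter open, and the investigator's calculation is made at the visit.

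The effect is limited to 5- and 6-entry weeks within the bands shown, and always favours remission under the 7-day rule. It concerns secondary outcomes only: the primary prevalence endpoint rests on histology, and the sample size is untouched. With about 30 MC patients, a few such weeks at one visit would be visible, at about 3.3 points each. The number of weeks affected is unknown. The classification bands follow from the stated rules alone; the Poisson figures rest on assumed rates and only illustrate the dependence on closeness to the threshold.

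**What to change.** Use one divisor for diary-based follow-up means. In the follow-up part of 7.1 and in 8.3.1, replace division by 7 with division by the number of evaluable days with entries. Refer to 7.2 for the 5-day rule and the preparation-day exclusion, so that an excluded day leaves both the count and the divisor.

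Keep division by 7 in two cases: the baseline interview, and flagged estimates of the full week when the diary is missing. A divisor requiring at least 5 diary days, applied throughout, would leave both without a valid mean, including the clinical activity at diagnosis that section 9.1 uses in the ROC analysis.

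The cost is a wording change in two sections and a check that the eCRF derivation matches. No extra patients or visits are needed.
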